10.4 Analysis of Vital Signs

Vital sign measurements of systolic and diastolic blood pressure, pulse rate, respiratory rate, body temperature and body weight will be summarized. Vital sign variables during the DBP, BEP and Safety Follow-up Period will be summarized, respectively.

Each vital sign variable will be summarized for all time points (starting with Baseline) with the number of non-missing observations, mean and standard deviation, median, minimum and maximum. Mean change from baseline to each planned time point, to the minimum, maximum, and final post-baseline value will be summarized for each vital sign variable, with the number of observations, baseline mean, and visit mean. The change from baseline mean, standard error, and 95% confidence interval will be presented for the mean change from baseline within each treatment group (modal daily dose for BEP).

Both the observed value and the change from baseline for vital sign variables will be evaluated based on PCS criteria (Appendix C). For each vital sign PCS criterion, the number and percentage of subjects who have at least 1 post-baseline observation that meets the PCS criterion will be summarized by treatment group (modal daily dose for BEP). A post-baseline value will be considered as a PCS value if it meets both the observed value and the change from baseline criteria. Listings of subject-level vital sign data will be provided for subjects meeting the criteria.

10.5 Other Safety Analyses

Other safety parameters include electrocardiograms, ophthalmologic examination, C-SSRS, and EPS scales (Simpson-Angus Scale [SAS], Abnormal Involuntary Movement Scale [AIMS] and Barnes Akathisia Rating Scale [BARS]).

10.5.1 Analysis of Electrocardiograms

ECG parameters of heart rate, PR interval, RR interval, QRS duration, QT interval, QTcB, and QTcF will be summarized.

Each ECG parameter will be summarized for all time points (starting with Baseline) with the number of non-missing observations, mean and standard deviation, median, minimum and maximum. Mean change from baseline to each planned time point, to the minimum, maximum, and final post-baseline value will be summarized with the number of observations, baseline mean, and visit mean. The change from baseline mean, standard error, and 95% confidence interval will be presented for the mean change from baseline within each treatment group (modal daily dose for BEP).

The criteria for PCS ECG parameters will be determined by list in Appendix C. For each ECG PCS criterion, the number and percentage of subjects who have at least 1 post-baseline observation that meets the PCS criterion and is more extreme than their baseline value will be summarized by treatment group (modal daily dose for BEP). Listings of subject-level ECG data will be provided for subjects meeting the criteria.

A listing of subjects with post-baseline significant ECG abnormalities as reported by the central laboratory will be provided.

A summary will also be provided showing subjects who have an increase in QTcB or QTcF from baseline of more than 30 msec but not exceeding 60 msec and subjects who have an increase of 60 msec or higher.

10.5.2 Ophthalmologic Examination

Ophthalmologic parameters include best corrected visual acuity (logMAR of each eye and the lower logMAR of 2 eyes) and the observed results of slit-lamp assessment (examination for abnormalities of the eyelid, conjunctiva, anterior chamber, cornea, vitreous chamber, iris, pupil, optic disc, retinal vessels, and macula). Ophthalmologic parameters during the DBP, BEP and Safety Follow-up Period will be summarized, respectively.

Each continuous ophthalmologic parameter and its change from baseline will be summarized for all time points (starting with Baseline) with the number of non-missing observations, mean and standard deviation, median, minimum and maximum.

A shift table from normal baseline to abnormal post-baseline in slit-lamp assessment results will be provided for all time points.

The criteria for potentially clinically significant (PCS) ophthalmologic parameters will be determined by list in Appendix C. For each ophthalmologic PCS criterion, the number and percentage of subjects who have at least 1 post-baseline observation that meets the PCS criterion and is more extreme than their baseline value will be summarized by treatment group (modal daily dose for BEP). Listings of subject-level ophthalmologic data will be provided for subjects meeting the criteria.

10.5.3 Columbia–Suicide Severity Rating Scale

For the C-SSRS, the number and percentage of subjects with any suicidal ideation or suicidal behavior as recorded on the C-SSRS will be presented by treatment group (modal daily dose for BEP) and by period (the lifetime history, DBP, BEP, and Safety Follow-up Period). The number and percentage of subjects with the most severe suicidal ideation and suicidal behavior during the lifetime history, DBP, BEP, and the Safety Follow-up Period will also be presented by treatment group (modal daily dose for BEP) and period. In addition, the number of percentage of subjects with non-suicidal self-injurious behavior will be summarized by treatment group (modal daily dose for BEP) and each period.

10.5.4 Extrapyramidal Symptom Scales

EPS parameters including SAS (total score), AIMS (total score) and BARS (total score) will be summarized.

These total scores are derived using the following formula: (total number of items in the scale) \times (sum of non-missing items divided by number of items with non-missing values).

- The SAS total score is the sum of the 10 items of the SAS. If more than 1 item for the SAS is missing, the total score will be set to missing.
- The AIMS total score is the sum of the first 7 items of the AIMS. If more than 1 item for the AIMS (items 1-7) is missing, the total score will be set to missing.
- The BARS total score is the sum of the first 3 items of the BARS. If any item for the BARS (items 1-3) is missing, the total score will be set to missing.

Each EPS parameter will be summarized for all time points (starting with Baseline) with the number of non-missing observations, mean and standard deviation, median, minimum and maximum. Mean change from baseline to each planned time point will be summarized with the number of observations, baseline mean, and visit mean. The change from baseline mean, standard error, and 95% confidence interval will be presented for the mean change from baseline within each treatment group (modal daily dose for BEP).

A subject will be considered to have treatment-emergent parkinsonism if the subject's SAS total score was ≤ 3 at baseline and > 3 at any post-baseline assessment.

A subject will be considered to have treatment-emergent akathisia if the subject's BARS total score was ≤ 2 at baseline and > 2 at any post-baseline assessment.

The number and percentage of subjects with treatment-emergent parkinsonism or akathisia will be tabulated by treatment group (modal daily dose for BEP). Listings of subjects with treatment-emergent parkinsonism or treatment-emergent akathisia will be provided.

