1.0 Introduction

This Statistical Analysis Plan (SAP) describes the methodology that will be used to summarize the statistical analyses of the efficacy and safety data for cariprazine Study M22-509's original protocol (version 1.0, 27Jan2022) and its most recent amendment (version 3.0, 25Jul2023).

The analyses pharmacokinetics (PK) endpoints will be analyzed separately and will not be covered in this SAP.

The Study M22-509 was early terminated as result of discussion due to an unexpected delay in enrollment. The main reasons for slow enrollment may include changes in the treatment environment with fewer relapses and exacerbations, difficulty obtaining informed consent due to washout of current antipsychotics during hospitalization, and the COVID-19 pandemic. Despite several protocol amendments to improve progress, approximately 30 subjects were enrolled (target: 250 subjects). 34 subjects were finally randomized at the time of early termination. The SAP will be part of the abbreviated CSR.

Unless noted otherwise, all analyses will be performed using SAS Version 9.4 (SAS Institute Inc., Cary, NC 27513) or later.

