7.1 Definitions of Baseline and Baseline Derived Variables

Unless otherwise specified, baseline is defined as the last non-missing value prior to the first administration of study drug for the DBP. For efficacy variables, baseline is defined as the non-missing value recorded at Visit 2.

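### A SAS form with one unrated item and a rated sum of 3 is prorated to 3.33 and crosses the parkinsonism cut-off, while a complete form with the same sum does not

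*SAP*

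**What the plan says.** SAP 10.5.4 builds the SAS total in three steps.

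- **Total:** "The SAS total score is the sum of the 10 items of the SAS".
- **Proration:** the number of items in the scale is multiplied by the "sum of non-missing items divided by number of items with non-missing values".
- **Missing-item limit:** "If more than 1 item for the SAS is missing, the total score will be set to missing". One blank item is therefore tolerated and the total is scaled up from nine.

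The same section calls a subject a case of treatment-emergent parkinsonism if the "SAS total score was ≤ 3 at baseline and > 3 at any post-baseline assessment". Cases are counted by treatment group (modal daily dose in the blinded extension period, BEP) and listed by subject.

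For safety scales, SAP 7.1 says "baseline is defined as the last non-missing value prior to the first administration of study drug for the DBP". No rounding rule appears in SAP 10.5.4, nor in SAP 9.1.1, which gives the same proration formula for efficacy scores.

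The other two scales in the section do not have the problem. For BARS, "If any item for the BARS (items 1-3) is missing, the total score will be set to missing", so the akathisia cut-off always meets a whole number. AIMS may be prorated but has no cut-off.

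**The concern.** The cut-off separates 3 from 4 on a scale that gives whole numbers when complete. Proration creates values between 3 and 4, and the rule then treats any such value as above 3. The only value that arises there is 3.33, from a rated sum of 3. In that case proration has in effect filled the blank with 0.33 of a point, which is nearer to 0 than to 1. The SAP's own estimate of the missing item does not point to a total of 4, yet the subject is classed as if it did.

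The error runs in both directions. After baseline it can create a case in which no item worsened, and one crossing at any assessment is enough. At baseline it gives 3.33, fails the at-or-below-3 condition, and takes the subject out of those who could become a case. The activity schedule (protocol Appendix D) has no SAS at screening, so there is normally no earlier rating to use instead. In any event the prorated value counts as non-missing.

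Extrapyramidal symptoms are an adverse event of special interest (protocol 6.1), and the SAS is a named safety endpoint (SAP 3.3).

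**Working it through.** **Inputs from the documents**

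- 10 SAS items, one blank allowed, proration formula, and cut-offs ≤ 3 and > 3: SAP 10.5.4.
- Post-baseline SAS ratings: six in the DBP (Weeks 1 to 6) and five in the BEP (Weeks 8, 12, 16, 20, 24): protocol Appendix D.
- Subjects: "34 subjects were finally randomized at the time of early termination" (SAP 1.0).

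The plan states no figure of its own to reproduce on this point.

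**Assumption.** SAS items are whole-number ratings starting at 0. The documents do not give the item range; a cut-off of 3 on a 10-item sum implies it.

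**Step 1. Nine items rated: total = 10 × sum / 9**

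| Rated sum | Complete form | One item blank | > 3 when complete? | > 3 with one blank? | Rounded total > 3? |
|---|---|---|---|---|---|
| 2 | 2 | 2.22 | no | no | no |
| 3 | 3 | 3.33 | no | **yes** | no |
| 4 | 4 | 4.44 | yes | yes | yes |

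Sums below 2 stay below the cut-off and sums above 4 stay above it. Only a rated sum of 3 changes class.

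**Step 2. True total 3, one item left blank at random.** The flag is false when the blank item would have scored 0. If it would have scored above 0, the prorated total is 2.22 or less and nothing is flagged.

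- Points on three items (1+1+1): 7 of 10 omissions give 3.33.
- Points on two items (2+1): 8 of 10.
- Points on one item (3): 9 of 10.

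**Step 3. Frequency in the DBP.** Assume that 5% to 10% of ratings total 3, that 0.5% to 5% of ratings have one blank item, that a share of 0.8 of the blanks fall on a zero item (middle of Step 2), that all ratings are obtained and that every baseline is at or below 3. Planned ratings: 34 × 6 = 204.

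- Low: 204 × 0.05 × 0.005 × 0.8 = 0.04 false crossings.
- High: 204 × 0.10 × 0.05 × 0.8 = 0.82.

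**Step 4. Effect of one misclassified subject.** Arm sizes are not stated. At an assumed 11 to 17 per arm, one subject moves an arm's incidence by 100/17 = 5.9 to 100/11 = 9.1 percentage points.

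**Step 5. What rounding loses.** For a true total of 4 and one item blank at random:

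| Item pattern | Flagged, unrounded | Flagged, rounded | Lost |
|---|---|---|---|
| 1+1+1+1 | 10 of 10 | 6 of 10 | 4 |
| 2+1+1 | 9 of 10 | 7 of 10 | 2 |
| 3+1 | 9 of 10 | 8 of 10 | 1 |
| 2+2 | 8 of 10 | 8 of 10 | 0 |
| 4 | 9 of 10 | 9 of 10 | 0 |

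**The case against.** The strongest reply is that this is an edge case of unknown frequency in a result that decides nothing. No hypothesis is tested on safety parameters (protocol 7.5), and the study stopped early and feeds an abbreviated report (SAP 1.0). Parkinsonism is also visible in SAS mean changes, in the parkinsonism cluster of special-interest terms (SAP Appendix B) and in rescue-medication use. Because cases are listed by subject, a lone borderline case can be inspected. All of this stands, and it keeps the point minor. The listing cannot, however, show a subject wrongly excluded by a baseline of 3.33.

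A second reply is that rounding is not neutral: it treats the blank as 0 and gives up some true cases, and preferring under-detection to over-detection in a safety count is a choice. That is fair, and Step 5 shows the cost. The case for rounding is that it follows the SAP's own fill-in value of 0.33 and restores the cut-off that applies to complete forms.

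The size estimate is also open to challenge. It counts crossings, while the SAP counts subjects, so a false crossing in someone who truly reaches 4 at another visit adds no case. It also leaves out the five BEP ratings, which would raise it. Both criticisms are right; the figure gives an order of magnitude only.

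A reader might infer that any unchanged SAS of 3 with one blank item becomes a case. It does not: 1 to 3 of the 10 possible omissions fall on a scored item and give 2.22 or less.

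**Conclusion.** The rule as written classifies the same rated sum of 3 differently according to whether one item is blank. When the blank item would have scored 0, it produces a false case after baseline or a false exclusion at baseline. That follows directly from SAP 10.5.4, given whole-number items starting at 0.

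The size is small and uncertain: fewer than one false crossing in the DBP even at the upper end of the assumed rates, with the BEP not counted. None may occur. If one does, it would move an arm by about 6 to 9 percentage points at 11 to 17 subjects per arm.

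It would be tempting to conclude that the reported parkinsonism incidence will be materially wrong, or that SAS totals are fractional in general. The documents support neither. They give no item-missing rate and no SAS distribution, and complete forms always give whole numbers. The akathisia definition, the mean-change tables and the efficacy results are unaffected. This is a cheap improvement to a stated rule, not a threat to any conclusion.

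**What to change.** Add one sentence to SAP 10.5.4: for the treatment-emergent parkinsonism definition only, a prorated SAS total is rounded to the nearest whole number before the ≤ 3 and > 3 cut-offs are applied, at baseline and after it. Keep the unrounded total for the mean-change tables. Rounding sends 3.33 to 3 and leaves every other rated sum in its present class. No ties arise, because tenfold ninths never end in exactly one half.

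The cost is one sentence and one line of code, settled before the single final database lock (SAP 11.0), plus the lost detections in Step 5. A true total above 4 can also be missed if the blank item carries all the points beyond 3. To keep this visible, mark in the subject listing anyone whose classification changes through rounding, including those reclassified at baseline.

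Setting the SAS total to missing when any item is blank, as the SAP does for BARS, would also remove the fraction, but it discards the whole rating, including forms with rated sums of 4 or more that are clearly above the cut-off.

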7.5 Statistical Analyses for Safety

Safety analyses for the DBP will be carried out using the safety population. The baseline value for safety analysis is the last non-missing measurement value collected on or before the first dosing date of study drug. For continuous safety outcomes, the change from baseline will be analyzed in a descriptive manner by treatment group and by visit. For categorical safety outcomes, the number and percentage of each category will be summarized by treatment group and by visit. Shift of laboratory values from baseline to defined time points will be tabulated. Hypothesis testing will not be performed for safety parameters.

Analysis of Adverse Events

All AEs will be coded using the current version of the Medical Dictionary for Regulatory Activities (MedDRA). The number and percentage of subjects with TEAEs, treatment-emergent SAEs, AEs with a reasonable possibility of being related to study drug, AEs leading to study drug discontinuation during the DBP will be summarized by treatment group and will be tabulated using the primary MedDRA system organ class and preferred term. TEAEs for the DBP will be defined as all events that begin or worsen on or after the first dose of DBP study drug and before the first dose of BEP study drug for subjects who participate in the BEP or within 30 days after the last dose of DBP study drug for subjects who do not participate in the BEP.

Analysis of Laboratory Data

Changes from baseline to each planned visit and to the minimum, maximum, and final value during the DBP will be summarized by n, mean, standard deviation, minimum value, median, and maximum value for each treatment group for each continuous hematology, chemistry, and urinalysis laboratory parameter.

Changes in laboratory parameters from baseline to the final value will be tabulated using shift tables by categories of low, normal, or high based on the normal ranges of the laboratory that performed the assay.

For each hematology, chemistry, and urinalysis laboratory parameter that potentially clinically significant (PCS) criteria are defined, a summary of the number and percentage of subjects who have at least 1 postbaseline observation that meets the PCS criterion and is more extreme than their baseline value will be provided for each treatment group.

Analysis of Vital Signs

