10.0 Safety Analyses

10.1 General Considerations

Safety data during the DBP and BEP will be summarized for the safety population and BEP population, respectively. Safety summaries during the DBP and BEP will be presented by treatment group (modal daily dose for BEP), including a total group for all subjects on active study treatment, respectively.

Safety data during the Safety Follow-up Period will be summarized for the safety population. The double-blind treatment subjects actually received during the DBP and modal daily dose during the BEP correspond to the treatment groups that will be used for summaries of safety data during the Safety Follow-up Period for subjects who did not enter the BEP and subjects who entered the BEP, respectively. The Safety Follow-up Period starts the day after the last dose of study drug in the study (either during the DBP or BEP).

Unless otherwise specified, safety data will be summarized by period.

For all safety endpoints, the data from subjects who were randomized to cariprazine 3 mg/day prior to removal of this dose arm from the DBP will be included in analyses of the DBP.

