10.2.1 Treatment-Emergent Adverse Events and Newly Emergent Adverse Events

Treatment-emergent AEs (TEAEs) are defined as any AE with an onset date that is on or after the first dose of study treatment and no more than 30 days after the last dose of study drug. TEAEs for the DBP will be defined as any AE with an onset date that is on or after the first dose of DBP study drug and before the first dose of BEP study drug for subjects who participate in the BEP, or on or before the last dose of DBP study drug for subjects who participate in the Safety Follow-up Period (and not in BEP), or within 30 days after the last dose of DBP study drug for subjects who do not participate in either BEP nor Safety Follow-up Period. TEAEs for the BEP will be defined as any AE with an onset date that is on or after the first dose of BEP study drug and on or before the last dose of BEP study drug for subjects who participate in the Safety Follow-up Period, and within 30 days after the last dose of BEP study drug for subjects who do not participate in Safety Follow-up Period. AEs during Safety follow-up are defined as any AE with an onset date during the Safety Follow-up Period after the DBP and BEP. All TEAEs will be summarized overall, as well as by primary MedDRA SOC and PT. The SOCs will be presented in alphabetical order, and the PTs will be presented in alphabetical order within each SOC. All AEs during Safety follow-up will also be summarized in the same manner as TEAEs.

Unless otherwise specified, TEAEs will be summarized during the DBP and BEP, respectively, and AEs during Safety follow-up will be summarized during the Safety Follow-up Period.

The number and percentage of subjects experiencing TEAEs will be summarized. The number and percentage of subjects experiencing AEs during Safety follow-up will be summarized.

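### In the extension-period tables, parkinsonism and akathisia that first appeared in the double-blind period and persist or recur are counted as emergent under the extension-period modal dose

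*SAP*

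**What the plan says.** SAP 7.1 sets a single default: "Unless otherwise specified, baseline is defined as the last non-missing value prior to the first administration of study drug for the DBP". The only exception given there is for efficacy variables, which use Visit 2. Protocol 7.5, written for the DBP, agrees in substance: "The baseline value for safety analysis is the last non-missing measurement value collected on or before the first dosing date of study drug".

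SAP 10.5.4 applies this baseline to two scale-based definitions. Parkinsonism is treatment-emergent if the "SAS total score was ≤ 3 at baseline and > 3 at any post-baseline assessment". Akathisia is treatment-emergent if the "BARS total score was ≤ 2 at baseline and > 2 at any post-baseline assessment". The section names no Week 6 or BEP baseline and does not say which visits belong to which period's count. It tabulates the results by treatment group, which for the BEP means the modal daily dose. SAP 10.1 adds: "Unless otherwise specified, safety data will be summarized by period".

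The treatment changes at the boundary. Under SAP 2.2, subjects on 6 mg/day move to 3 mg/day and placebo subjects move to 1.5 mg/day. Elsewhere the SAP keeps the periods apart. In 10.2.1 a BEP treatment-emergent event is "any AE with an onset date that is on or after the first dose of BEP study drug" (with an end limit), and in 9.4.5 the BEP efficacy endpoints are measured from both baseline and Week 6.

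**The concern.** The BEP table will be read as showing how often parkinsonism and akathisia emerged during the extension at each modal dose. The rule does not measure that. A subject who was at or below the cut-off on Day 1, crossed it in the DBP and stays above it at Week 8 enters the BEP table as an emergent case under the BEP modal dose. For a former placebo subject, the case is attributed to cariprazine whatever the modal dose, since every BEP dose is active.

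Akathisia and extrapyramidal symptoms are adverse events of special interest (Protocol 6.1; SAP 10.2.5). The BEP report would therefore hold two sets of counts labelled treatment-emergent for akathisia, one based on onset within the BEP and one not. With 34 subjects randomized (SAP 1.0) and only descriptive safety summaries, the raw percentages are the result, and one subject can move a modal-dose group visibly.

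**Working it through.** The documents state no figure on this point, so there is none to reproduce. The check applies the rule to hypothetical BARS profiles and then illustrates the size with assumed rates.

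**Three readings of the BEP count**

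(a) Literal: at or below 2 before the DBP, above 2 at any later visit, including DBP visits.
(b) Same baseline, BEP visits only. SAP 10.1 implies this, but 10.5.4 does not say it.
(c) At or below 2 at Week 6, above 2 at a BEP visit.

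| Hypothetical subject | (a) | (b) | (c) |
|---|---|---|---|
| 0 on Day 1; 3 from Week 2 to Week 6; still 3 at Week 8 | counted | counted | not counted |
| 0 on Day 1; 4 at Week 2; 0 by Week 5 and throughout the BEP | counted | not counted | not counted |
| 0 throughout the DBP; 3 at Week 12 | counted | counted | counted |
| 0 on Day 1; 3 in the DBP; 0 at Week 6; 3 again at Week 12 | counted | counted | counted |
| 0 on Day 1; 3 at Week 6; 5 at Week 12 | counted | counted | not counted |
| 4 on Day 1; 1 at Week 6; 3 at Week 12 | not counted | not counted | counted |
| 0 at every visit | not counted | not counted | not counted |

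The first row is the problem: a case that began in the DBP and persisted is emergent in the BEP under both readings of the current text. The second row shows that (a) and (b) give different tables, so two programmers could disagree. The fifth row shows what (c) alone would hide: worsening of a case already present at Week 6. The sixth shows a case that the current rule can never count.

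**Illustration of size (all rates assumed)**

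Let n = 15 be the size of a modal-dose group, with everyone at or below the cut-off before the DBP. Let p = 0.20 be the proportion with onset in the DBP, s = 0.50 the share of those still above the cut-off at Week 6 and at a BEP visit, and q = 0.10 the proportion with new onset in the BEP among those not already above the cut-off. For (a), q applies to subjects without DBP onset.

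- (a) p + (1 − p)q = 0.20 + 0.80 × 0.10 = 0.28, or 15 × 0.28 = 4.2 subjects.
- (b) ps + (1 − ps)q = 0.10 + 0.90 × 0.10 = 0.19, or 15 × 0.19 = 2.85 subjects.
- (c) (1 − ps)q = 0.90 × 0.10 = 0.09, or 15 × 0.09 = 1.35 subjects.

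If the denominator for (c) is the subjects at or below the cut-off at Week 6, it is 15 × 0.90 = 13.5, and 1.35 / 13.5 = 10%, which recovers q.

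Over p from 0.10 to 0.30, s from 0.25 to 0.75 and q from 0.05 to 0.10, reading (b) gives 7% to 30% and reading (c) 4% to 10% of all n.

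Each carried-over case adds 1/15 = 6.7 percentage points to a group of 15, or 1/10 = 10 points to a group of 10. Both group sizes are assumptions.

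**The case against.** A pre-treatment baseline is a coherent convention. The SAP uses it throughout its safety sections, including laboratory values, vital signs, ECG and ophthalmology (10.3 to 10.5.2). On that reading, treatment-emergent means absent before any study drug and present on treatment. For former active-arm subjects, Week 6 is an on-drug value, so switching to it outright would drop cases that persist or worsen. This stands, and it is why the existing count should be kept.

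Other parts of the plan soften the point. SAP 10.2.5 already summarizes akathisia and other extrapyramidal events as adverse events under the period-specific onset rule. SAP 10.5.4 also promises subject listings and score summaries at every time point. With 34 subjects, case-by-case review is feasible, although the listing contents are not specified.

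A reader might infer that every case from the DBP is carried into the BEP table, or that events arising at 6 mg/day are systematically charged to lower doses. The documents support neither. The period split in SAP 10.1 implies that only BEP visits count, in which case resolved cases drop out. Protocol 4.1 allows escalation back to 6 mg/day, so the BEP modal dose can equal the DBP dose. For subjects from the removed 3 mg/day arm, whom the SAP retains, the BEP starting dose is not stated in the documents. Modal-dose grouping also blurs attribution within the BEP, and no choice of baseline cures that. Nor do the adverse-event and scale tables contradict each other: one counts events by onset date, the other counts threshold crossings.

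What remains is that the BEP scale table, as specified, mixes carried-over and new cases, and nothing in 10.5.4 separates them.

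**Conclusion.** The point holds in limited form. With the pre-DBP baseline and no limit on assessments, the BEP count includes subjects whose SAS or BARS first crossed the cut-off in the DBP and is still, or again, above it at a BEP visit. They are tabulated under their BEP modal dose, including cases that arose on placebo or on 6 mg/day. The onset rule for BEP adverse events would not attribute a persisting case in this way.

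The size is unknown. The documents give neither the carry-over at Week 6 nor the modal-dose group sizes, and carry-over could be zero. The 19% against 9% is an illustration only. The primary and key secondary endpoints are unaffected. What is affected is the period and dose attribution of an adverse event of special interest in a small descriptive table. The pre-DBP count is not an error in itself; it should not be the only BEP count, or be left without a label saying what it measures.

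**What to change.** In SAP 10.5.4:

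1. State that DBP counts use DBP assessments only and BEP counts use BEP assessments only.
2. For the BEP, add a count of subjects with SAS ≤ 3 (parkinsonism) or BARS ≤ 2 (akathisia) at the last assessment before the first BEP dose, normally Week 6 (Visit 8), and above the same cut-off at a BEP assessment. The denominator for each is the subjects at or below that cut-off at that point.
3. Keep the count against the pre-DBP baseline, labelled as cumulative since first study drug, so that cases persisting, worsening or recurring from the DBP stay visible.

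No new data are needed. Protocol Appendix D schedules SAS and BARS at Week 6 and at Weeks 8, 12, 16, 20 and 24, and Protocol 4.1 places the Week 6 activities before the switch to BEP treatment. The cost is a few sentences in the SAP and one extra small descriptive table.
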